## STUDY SUMMARY

**TITLE** **AI-assisted diagnosis and prognostication in COVID-19**

**DESIGN** Retrospective data study on patients with suspicious and confirmed COVID-19.

**AIMS** To investigate whether computer-based analysis (machine learning) enable the diagnosis of Covid-19 primarily on ECGs, but also from CXR and CT images

**OUTCOME MEASURES** Accuracy with which computer based analysis (machine learning) can diagnose and/or prognosticate Covid-19 infection primarily from ECG, but also from chest xray and CT images

**POPULATION** The study aims to collect data from up to 2000 patients at Chelsea and Westminster Hospital NHS Foundation Trust, Imperial College Healthcare NHS Trust and London North West London University Healthcare NHS Trust, from 15 May 2020.

**ELIGIBILITY** To be included in this study the patient must:

- have ECGs, Chest x-ray and/or chest CT imaging (with or without contrast)
- laboratory Covid-19 virus nucleic acid test (RTPCR assay with throat swab samples) or clinical suspicion for Covid-19 infection
- be aged >18 years

**DURATION** 2 years

## 1. INTRODUCTION

### 1.1 BACKGROUND

Coronavirus Disease 2019 (COVID-19) has been widespread worldwide since December 2019 [1] [2]. It is highly contagious, and severe cases can lead to acute respiratory distress or multiple organ failure [3]. On 11 March 2020, the WHO made the assessment that COVID-19 can be characterised as a pandemic. As of 25 March 2020, in total, 416, 916 cases of COVID-19 have been recorded, and the death toll has reached 18,565 with a rapid increase of cases in Europe and North America.

The disease can be confirmed by using the reverse-transcription polymerase chain reaction (RT-PCR) test [4]. While being the gold standard for diagnosis, confirming COVID-19 patients using RT-PCR is time-consuming, and both high false-negative rates and low sensitivities (60-95%) may put hurdles for the presumptive patients to be identified and treated early [3][5][6]. With infected patients and tested individuals steadily increasing, health care systems are overwhelmed by the unprecedented testing frequencies and massive patient loads. Thus, the situation presents a diagnostic dilemma with patients showing non-specific symptoms, as well as RT-PCR assays often being unavailable and known for high false negative rates.

As non-invasive electrocardiographic (ECG) recordings and imaging techniques, such as computed tomography (CT) and chest X-ray (CXR) can detect those characteristics, e.g., myocarditis, bilateral patchy shadows or ground glass opacity (GGO), manifested in the COVID-19 [7][8]. Hence ECG, CT and CXR may serve as an important tool for COVID-19 to be screened, diagnosed and prognosticated early.

### 1.2 RATIONALE FOR CURRENT STUDY

Coronavirus Disease 2019 (COVID-19) has been widespread worldwide since December 2019. It is highly contagious, and severe cases can lead to acute respiratory distress or multiple organ failure and ultimately death. The disease can be confirmed by using the reverse-transcription polymerase chain reaction (RT-PCR) test. ECGs, Chest x-rays and CT scans are rich sources of data that provide insight to disease that otherwise would not be available. Knowing who to admit to the hospital or intensive care saves lives as it helps to mitigate resource shortages. Novel Artificial Intelligence tools such as Deep learning will allow a complex assessment of the Imaging and clinical data that could potentially help clinicians to make a faster and more accurate diagnosis, better triage patients and assess treatment response and ultimately better prediction of outcome.

Our group has significant experience implementing machine learning algorithms on vast quantities of ECGs, such as from the UK Biobank, and propose to extend our techniques to data from patients with Covid-19.

ECGs are routinely performed on unwell patients presented to hospital and often have serial recordings during their inpatient stay. This provides a unique method by which disease progression can be tracked using a simple, non-invasive and inexpensive method throughout the course of the illness. Furthermore, whether COVID-19 causes specific ECG changes is not known. Identifying and understanding ECG changes related to COVID-19, particularly those features that may predict clinical outcomes, would be especially useful. The non-invasive, quick and easy nature of recording ECGs in unwell patients makes it an ideal modality to investigate and predict COVID-19 related outcomes.

As the manifestation of COVID-19 and related complications on ECG is currently unknown, we hypothesise that beyond routine radiographic imaging, ECG can provide an insight into clinical outcomes related to COVID-19 that can be helpful for prognostication.

Imaging of COVID-19 is performed with CXR and CT. Chest radiograph is the initial screening imaging tool in patients with suspicious clinical symptoms of COVID-19 (including fever and lymphopenia). Radiographic appearances are of symmetric patchy or diffuse airspace opacities. Typical CT appearances include peripheral, bilateral ground glass opacity (GGO) which may have a rounded morphology, with or without consolidation. A crazy-paving pattern can be seen with ground glass opacity and intralobular lines. Imaging features depend on when infected patients are imaged. Up to approximately 50% of patients with COVID-19 infection may have normal CT scans 0–2 days after onset of flu-like symptoms [18]. GGO opacity usually develops between day 0 and 4 after symptom onset. The frequency of consolidation increases later in the course of the disease, peaking at 6–13 days with higher rates of bilateral and multilobar involvement. An organising pneumonia pattern is observed with reverse halo or atoll sign and perilobular opacities. About 2–3 weeks after the onset, CT may show varying degrees of clearing of the patchy consolidative opacities, reticular opacities, bronchial wall thickening, and interlobular septal thickening [9]. Imaging (CXR & CT) may be used as an aid in diagnosing COVID-19, guide individual patient management decisions, deal with complications or look for an alternative diagnosis.

With the development of machine learning, deep learning based artificial intelligence (AI) technology has demonstrated tremendous success in the field of medical data analysis due to its capacity of extracting rich features from imaging and complex clinical datasets [10]. Recently, deep learning has been used for diagnosing and distinguishing bacterial and viral pneumonia from thoracic imaging data [11]. In addition, attempts have been made to detect various ECG and chest CT imaging features [12]. In the current COVID-19 pandemic, some preliminary studies have shown promising results for the ECG, chest CT and CXR data analysis and classification [2][3][13]. Besides, small scale initial studies have been done for COVID-19 monitoring [14], screening [15] and prediction of the hospital stay [16].

Exploring the added value of artificial intelligence-assisted disease detection and characterisation may potentially help clinicians to make a prompt correct diagnosis, guide treatment and predict prognosis.

We hypothesise ECGs, CXR and CT scans from patients with confirmed or suspected COVID-19 infection can be used to develop machine learning algorithms that will subsequently diagnose and predict the clinical course of the infection in other patients as well. Furthermore, we believe machine learning and artificial intelligence when applied to ECG, CXR and CT can evaluate the effect of COVID-19 on heart function and more accurately diagnose and prognosticate infection than doctors.

## 2. STUDY OBJECTIVES

### Primary objectives

- We will investigate if the standard electrocardiogram (ECG), which is a conventional clinical tool used record the electrical activity of the heart, a chest X-ray and/or a CT scan, can be used to predict the course and severity of disease in patients with Coronavirus Disease 2019 (COVID-19).

### Secondary objectives

- We will also investigate if the standard electrocardiogram (ECG), which is a conventional clinical tool used to record the electrical activity of the heart, a chest X-ray or a CT scan, can be used in patients with Coronavirus Disease 2019 (COVID-19) to predict subsequent heart involvement due to the infection.
- We will assess if computer-based analyses are better than doctors at diagnosing features of COVID-19 infection.

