#### 3.1 STUDY OUTCOME MEASURES

The accuracy with which computer based analysis (machine learning) can diagnose and/or prognosticate Covid-19 infection primarily from ECG, but also from chest xray and CT images.

To determine if computer based analysis (deep learning) enables assessment of the effect of COVID-19 on heart function.

To determine if AI system is superior to cardiology/medical team and/or radiologist assessment.

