### 4. PARTICIPANT ENTRY

#### 4.1 PRE-REGISTRATION EVALUATIONS

Clinical data will be reviewed by a member of the clinical team and the following clinical and laboratory data will be recorded:

- Gender
- Age
- Height/Weight, body mass index
- Medical history (diabetes, hypertension, coronary heart disease, malignancy, structural lung disease, pulmonary heart disease, chronic liver disease, immunosuppressed population)
- The duration of symptoms at the first visit (days, could be inquired from the main complaint of the patient at the first visit, symptoms including fever, dry cough, headache, myalgia, weakness, etc.)

- Smoking status (Never = 0, Ex-smoker = 1, Current = 2, Unknown = 3)
- Pack Years History
- Current NSAID use
- Current ACEi use
- Current Angiotensin receptor blocker use
- Respiratory rate (breaths/min)
- Heart Rate
- Blood Pressure
- Temperature
- Clinical Classification
- oxygen saturation at a rest state (%)
- arterial partial pressure of oxygen (PaO2)/oxygen concentration (FiO2, mmHg)
- Recovery/Death
- Time/date of the CT scanning
- Time/date of the Chest x ray
- D-dimer
- White blood cell count
- Lymphocyte cell count
- platelet count
- C-reactive protein
- Troponin T
- ALT, AST, ALB, ESR, CD3, CD3 count, CD4, CD4 count, CD8, CD8 count, CD19, CD19 count, IL-6, IL-8, IL-10, TNF- $\gamma$
- RT-PCR results for SARS-Cov 2 (Date, results)
- Stay at ICU (days)
- Hospital Stay (days)
- Date of death
- Cause of death
- Intubation
- Date of Intubation
- Time mechanical Ventilation (days)
- NEWS score on arrival

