#### 4.3 EXCLUSION CRITERIA

The presence of any of the following will preclude the patient from the study:

1. Suboptimal ECGs, chest radiographs or CT studies for deep learning methods due to artefacts including severe motion artefacts which causes blurring of the contours of or significant artefacts due to metallic prosthesis which causes image degradation
2. Time-interval between ECGs, chest CT and the RT-PCR assay was longer than 7 days

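### The plan attributes heart involvement to COVID-19 but collects too little about the heart before the illness to separate prior heart disease from a COVID-19 effect

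*Combined protocol and SAP*

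**What the plan says.** The second half of the claim is causal in both places where it appears. Under Secondary objectives (Section 2), the ECG, chest X-ray or CT is to be used "to predict subsequent heart involvement due to the infection". Section 3.1 lists as an outcome measure: "To determine if computer based analysis (deep learning) enables assessment of the effect of COVID-19 on heart function". Neither place defines heart involvement or heart function by a measure, cut-off or time window.

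The data to support this are set out in Section 4.1. The history item reads "Medical history (diabetes, hypertension, coronary heart disease, malignancy, structural lung disease, pulmonary heart disease, chronic liver disease, immunosuppressed population". Age is recorded, and so is Troponin T, but no sampling time, threshold or endpoint role is given for Troponin T. Dates are listed for the CT and the chest X-ray but not for the ECG.

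On timing, the second exclusion criterion in Section 4.3 reads "Time-interval between ECGs, chest CT and the RT-PCR assay was longer than 7 days". Section 1.2 notes that patients "often have serial recordings during their inpatient stay" and says of this: "This provides a unique method by which disease progression can be tracked". Section 6 describes training algorithms to tell groups of patients apart, with ECG features given as examples.

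**The concern.** To say that a heart finding was caused by an infection, one needs some evidence that it was not there before. The planned data begin with the illness. A patient with long-standing atrial fibrillation, bundle-branch block, a pacemaker or heart failure has an abnormal ECG on arrival whatever the virus does. Such patients may also fare worse. An algorithm could therefore perform well partly by recognising chronic heart disease, and the report could describe that performance as detecting or predicting COVID-19 heart involvement. Nothing in the plan would show whether this had happened.

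**Working it through.** The documents give no event rate, effect size or power calculation, and the 2000 patients in Section 3 are a ceiling without inputs. There is thus no planned figure to reproduce. The check is mainly a comparison of what attribution needs with what the plan supplies.

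**What could separate old from new**

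- *A tracing from before the illness.* None is requested. The serial tracings in Section 1.2 are inpatient recordings, so they show change during the stay but not the state before it.
- *A recorded cardiac history.* Coronary heart disease, pulmonary heart disease and hypertension are listed in Section 4.1. Arrhythmia, conduction disease, paced rhythm, heart failure, cardiomyopathy and valve disease are not.
- *Exclusion of patients with prior heart disease.* Section 4.3 covers only artefact and timing. Its reference to "significant artefacts due to metallic prosthesis which causes image degradation" concerns image quality and does not remove patients with paced rhythm.
- *A recognisable COVID-19 pattern.* Section 1.2 says "whether COVID-19 causes specific ECG changes is not known". By the protocol's own account there is no established signature to rely on.
- *An analysis that handles prior disease.* Section 6 states no adjustment, restriction or comparison with an earlier tracing. The temporal stability it mentions is variation between heartbeats, not between earlier and later ECGs.

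None of the five routes is secured. The second is partly available but unused.

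**Illustration of size (all rates assumed)**

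Let p be the share of patients with a prior abnormality and n the share who develop a new one, taken as independent. Suppose that any abnormality counts as heart involvement. The flagged share is p + n(1 − p).

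- If patients with both are classed as old, the old share is p / [p + n(1 − p)].
  - p = n = 10%: 0.10 / 0.19 = 53%.
  - p = 5%, n = 20%: 0.05 / 0.24 = 21%.
  - p = 20%, n = 5%: 0.20 / 0.24 = 83%.
- If patients with both are classed as new, the old share is p(1 − n) / [n + p(1 − n)].
  - p = n = 10%: 0.09 / 0.19 = 47%, which in 2000 patients is 180 of 380 flagged.
  - With n from 5% to 20% and p from 5% to 30%, the range is 17% (0.04 / 0.24) to 85% (0.285 / 0.335).
- Under the second convention, suppose the recorded history identified half of the prior disease and the analysis used it. At p = n = 10% the share becomes 0.045 / 0.145 = 31%, or 90 of 290. Over the same grid it runs from 9% to 74%.

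These results show only that the old share need not be small. They are not estimates for this study.

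**The case against.** The strongest reply is that the plan does not commit the error. A reader might infer that old heart disease will be counted as an effect of COVID-19, or that heart involvement is to be read off the ECG. The documents support neither reading. The secondary objective makes the ECG, X-ray or CT the predictor of something later, and that later outcome is undefined. If it were based on a later Troponin T, a chronic ECG abnormality would not count directly. This stands: misattribution is an open risk, not a written rule. It does not rescue the causal wording, because nothing in the plan prevents the error either.

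Second, some protection exists. Age, hypertension, coronary heart disease and pulmonary heart disease are recorded and could be adjusted for. Rhythm, conduction and pacing are visible on a 12-lead ECG. This stands in part: no such adjustment is planned, and a single tracing shows that an abnormality is present, not how long it has been there.

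Third, Section 6 works by example, so it would be wrong to say that within-patient analysis is ruled out. That is correct. The fair statement is that the use of serial tracings for this purpose is unspecified.

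Fourth, for prognosis chronic heart disease is a legitimate predictor, and an algorithm that detects it has made no mistake. This is accepted, and it limits the point to the causal claims.

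Finally, a remedy that simply defines heart involvement as ECG change could use one tracing as both predictor and outcome. Read literally, the 7-day criterion in Section 4.3 could also exclude a patient because of an archived ECG. Both objections are sound, and the fix below allows for them.

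**Conclusion.** The concern holds in limited form. As written, the plan cannot support attributing heart involvement to the infection, because prior heart disease cannot be reliably separated from a COVID-19 effect. This touches one secondary objective and one outcome measure. It leaves the primary objective, predicting course and severity, intact. The conclusion rests on the text alone: no pre-illness tracing, an incomplete cardiac history, and no planned analysis that deals with prior disease. Its numerical size cannot be derived from the documents. The percentages above depend on assumed rates, on independence, and on every abnormality being counted, which the protocol does not say. They should be left out of any summary or labelled as an illustration. The matter should be settled before data extraction, since it changes what the study can conclude about the heart.

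**What to change.** 1. Add prior arrhythmia, conduction disease, paced rhythm, heart failure, cardiomyopathy and valve disease to the list in Section 4.1.
2. Report the heart-involvement results in patients without known heart disease alongside those in all patients.
3. Before anonymisation, retrieve the latest pre-illness ECG where one exists. State that this baseline tracing is exempt from the 7-day criterion in Section 4.3 and may predate the study's start date. Report how many patients have one. In that subgroup, wherever an ECG abnormality counts as heart involvement, count only what is new relative to the baseline.
4. If ECG change is used as an outcome, take it from a tracing later than the predictor ECG, so that one tracing does not serve as both. This requires the date and time of each ECG, which Section 4.1 does not list.
5. Where no earlier ECG can be used, replace the causal phrases in the secondary objective and in Section 3.1 with 'associated with', and align the matching hypothesis at the end of Section 1.2.

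The cost is a few more extraction fields and an archive query at the three Trusts. Earlier ECGs will exist for only some patients. That subgroup will be smaller and selected, probably towards older patients, so its results belong beside the full-cohort results and do not replace them. The change of wording costs nothing.

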### 3. STUDY DESIGN

This is a retrospective observational study on patients with suspicious and confirmed COVID-19.

The study aims to recruit up to 2000 patients who will be referred to have ECGs, chest X-rays or CT scans at Chelsea and Westminster Hospital NHS Foundation Trust, Imperial College Healthcare NHS Trust and London North West London University Healthcare NHS Trust, since 1 February 2020.

Patients with suboptimal ECGs, chest radiograph and CT studies due to artefacts will be excluded.

The study will gather data retrospectively and therefore data collection will cease once the prespecified number of participants is reached.

#### 3.1 STUDY OUTCOME MEASURES

The accuracy with which computer based analysis (machine learning) can diagnose and/or prognosticate Covid-19 infection primarily from ECG, but also from chest xray and CT images.

To determine if computer based analysis (deep learning) enables assessment of the effect of COVID-19 on heart function.

To determine if AI system is superior to cardiology/medical team and/or radiologist assessment.

### 4. PARTICIPANT ENTRY

#### 4.1 PRE-REGISTRATION EVALUATIONS

Clinical data will be reviewed by a member of the clinical team and the following clinical and laboratory data will be recorded:

- Gender
- Age
- Height/Weight, body mass index
- Medical history (diabetes, hypertension, coronary heart disease, malignancy, structural lung disease, pulmonary heart disease, chronic liver disease, immunosuppressed population)
- The duration of symptoms at the first visit (days, could be inquired from the main complaint of the patient at the first visit, symptoms including fever, dry cough, headache, myalgia, weakness, etc.)

- Smoking status (Never = 0, Ex-smoker = 1, Current = 2, Unknown = 3)
- Pack Years History
- Current NSAID use
- Current ACEi use
- Current Angiotensin receptor blocker use
- Respiratory rate (breaths/min)
- Heart Rate
- Blood Pressure
- Temperature
- Clinical Classification
- oxygen saturation at a rest state (%)
- arterial partial pressure of oxygen (PaO2)/oxygen concentration (FiO2, mmHg)
- Recovery/Death
- Time/date of the CT scanning
- Time/date of the Chest x ray
- D-dimer
- White blood cell count
- Lymphocyte cell count
- platelet count
- C-reactive protein
- Troponin T
- ALT, AST, ALB, ESR, CD3, CD3 count, CD4, CD4 count, CD8, CD8 count, CD19, CD19 count, IL-6, IL-8, IL-10, TNF- $\gamma$
- RT-PCR results for SARS-Cov 2 (Date, results)
- Stay at ICU (days)
- Hospital Stay (days)
- Date of death
- Cause of death
- Intubation
- Date of Intubation
- Time mechanical Ventilation (days)
- NEWS score on arrival

#### 4.2 INCLUSION CRITERIA

To be included in this study the patient must:

- have ECGs, Chest x-ray and/or chest CT imaging (with or without contrast)
- positive laboratory Covid-19 virus nucleic acid test (RTPCR assay with throat swab samples) or clinical suspicion for Covid-19 infection
- be aged >18 years

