## **5. ASSESSMENT AND FOLLOW-UP**

This is a retrospective data study and therefore there will be no follow-up. Therefore, there will be no assessments.

As all clinical data will be anonymised, incidental findings will not be reviewed or reported back to individuals or their GP or clinical care teams.

The study will end when the last pseudo-anonymised image has been segmented and ECG feature extracted, and the deep learning algorithm has been trained and validated.

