## **6. STATISTICS AND DATA ANALYSIS**

Machine learning algorithms will be trained to differentiate between patient groups (e.g. based on diagnosis or prognosis). For example, for the ECG analyses, in addition to conventional morphological features of QRS, we propose to analyse both temporal and spectrum features of the 12-lead ECG. The spectrum features would include band-powers of different frequency bands, and coefficients of auto-regression (AR) models of different orders would be used as temporal features. Moreover, the temporal stability of features (i.e., how the features vary from beat to beat) and the spatial dispersion of these features (i.e., who the features vary across the 12 leads) will also be investigated.

Data will be analysed by the chief investigator and the research team at the National Heart and Lung Institute, Imperial College London. Anonymised data may be shared with collaborators, for example at University College London, for data processing subject to any required data sharing agreements/approval being in place before the data is transferred.

Data and all appropriate documentation will be stored for a minimum of 10 years after the completion of the study, including the follow-up period.

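### Contrast and non-contrast chest CT are pooled, contrast use and scan indication are not listed data items, and no check is planned on whether CT accuracy partly reflects contrast use

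*Combined protocol and SAP*

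**What the plan says.** Four parts of the protocol bear on this.

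- **Eligibility.** Section 4.2 asks that patients "have ECGs, Chest x-ray and/or chest CT imaging (with or without contrast"). The Study Summary repeats this. Section 4.3 excludes CT for artefact or for too long an interval from the RT-PCR test; contrast is not a ground for exclusion.
- **Recorded data.** Section 4.1 states that "the following clinical and laboratory data will be recorded". The only item specific to CT is "Time/date of the CT scanning". Contrast use, scan protocol and scan indication do not appear.
- **Reasons for imaging.** Section 1.2 says that chest X-ray and CT may help in diagnosis and may also "guide individual patient management decisions, deal with complications or look for an alternative diagnosis".
- **Analysis.** Section 6 says "Machine learning algorithms will be trained to differentiate between patient groups (e.g. based on diagnosis or prognosis"). It details features for the ECG only, and gives no stratification, adjustment or sensitivity analysis by contrast.

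On the standing of CT, section 3.1 measures accuracy "primarily from ECG, but also from chest xray and CT images". The primary objective in section 2 nevertheless names CT beside ECG and chest X-ray for predicting course and severity, and section 3.1 also compares the AI system with radiologists.

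**The concern.** Intravenous contrast changes the appearance of a CT image whatever the state of the lungs. An algorithm trained on pooled images can use any visible feature that differs between the groups it is asked to separate. If contrast were given more often in one group, the algorithm could score above chance by detecting contrast. The pooled CT accuracy would then mix two things: recognition of lung disease, and recognition of how, and perhaps why, the scan was done.

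The protocol's account of why patients are imaged makes this plausible. Looking for another diagnosis bears on the diagnostic label, and dealing with complications bears on severity. If the choice of contrast depends on the clinical question, it could be associated with either label.

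At stake is the interpretation of the CT accuracy figure, and of any comparison with radiologists that uses it. The ECG result is not touched.

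**Working it through.** The plan states no figure to reproduce. It gives a ceiling of up to 2000 patients (section 3), with no number expected to have CT, no contrast rates and no target accuracy. The check therefore has two parts: reading the sections against each other, and an illustration on assumed rates.

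**Reading.** Section 4.2 admits both scan types. Section 4.3 does not restrict them, section 4.1 does not list which type each patient had, and section 6 does not separate them. No section says that contrast use differs between outcome groups, and none says that it does not.

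**Size of a contrast-only signal.** Let p1 and p0 be the shares of contrast scans in the two groups being separated. For a yes/no marker, counting ties as one half,

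AUC = p1(1 − p0) + ½[p1·p0 + (1 − p1)(1 − p0)] = 0.5 + (p1 − p0)/2,

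or 0.5 + |p1 − p0|/2 when the marker is read in the favourable direction. With 50% v 30%: 0.5 × 0.7 + ½(0.15 + 0.35) = 0.35 + 0.25 = 0.60.

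| Assumed contrast share, group 1 v group 0 | AUC from contrast alone |
|---|---|
| 30% v 30% | 0.50 |
| 40% v 30% | 0.55 |
| 50% v 30% | 0.60 |
| 60% v 20% | 0.70 |

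All the shares are assumptions. The first row matters as much as the others: with equal shares, contrast alone carries no information about the outcome.

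**Would recording contrast reveal an imbalance?** Take a two-sided test at 0.05 with equal groups of n each. With the pooled variance under the null,

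power = Φ{[|p1 − p0| − 1.96·√(2p̄(1 − p̄)/n)] / √([p1(1 − p1) + p0(1 − p0)]/n)}.

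For 50% v 30% with 250 CT patients (n = 125, p̄ = 0.40): (0.2 − 1.96 × 0.0620)/0.0607 ≈ 1.29, so power is about 90%.

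| CT patients in total | Power, 40% v 30% | Power, 50% v 30% |
|---|---|---|
| 100 | 18% | 53% |
| 250 | 38% | 90% |
| 500 | 65% | over 99% |

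A contrast field would thus show a large imbalance at moderate numbers of scans. A 10-point imbalance could easily be missed by a test, so the table of contrast by outcome group and the stratified accuracies should be reported whatever the test shows.

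**The case against.** The strongest reply has four parts.

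**The check is still possible.** A reader might infer that, because contrast is not listed, its effect can never be examined. The documents do not support that. The list in section 4.1 covers clinical and laboratory data and is not an inventory of image metadata. Section 5 says "The study will end when the last pseudo-anonymised image has been segmented", so the team holds the images and someone could label contrast from them. Whether scan headers survive pseudo-anonymisation is not stated. This part of the reply stands: what is missing is a listed item and a planned check, not the possibility of one.

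**The link from contrast to outcome is inferred.** A reader might take section 1.2 to show that contrast tracks diagnosis or severity. It does not mention contrast, and its sentence on uses covers chest X-ray and CT together. Nor do the documents say how contrast use varies within a Trust or scanner, so they cannot settle whether validation by site would deal with it. This also stands, and the link must be labelled as an assumption.

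**The AUC values do not measure inflation.** They describe a marker that sees contrast and nothing else. A model that already reads lung changes may gain much less. This stands.

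**CT is a lesser modality.** The outcome measure puts ECG first, CT is optional under section 4.2, and section 6 describes no CT features. Contrast is also only one of several possible image shortcuts, and the plan states no subgroup or shortcut check for any modality. This limits the weight but does not remove the point, because CT is named in the primary objective and in the comparison with radiologists.

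**Conclusion.** The point holds in a limited form. The protocol deliberately pools contrast and non-contrast CT, lists neither contrast nor indication among its data, and plans no analysis that would show whether CT accuracy depends on contrast. It does not follow that the CT result is biased.

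Bias through this route requires contrast use to differ between the outcome groups, and its size depends wholly on that unknown difference. Contrast alone would give an AUC between 0.50 (no difference) and 0.70 (60% v 20%) over the assumed range. These values are a yardstick for judging the reported CT accuracy, not an amount to subtract from it.

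The change is worth making because it is cheap and makes the CT result easier to interpret. It is of modest importance for the study as a whole, whose outcome measure is mainly about the ECG.

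**What to change.** **Section 4.1:** add CT contrast (yes/no), and scan indication where available, taken from existing scan records. Indication is the underlying variable and contrast only a proxy for it, so both are useful. Extract them before pseudo-anonymisation, since the protocol does not say what scan information is kept afterwards.

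**Section 6:** for each outcome that CT is used to classify,

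- tabulate contrast use by outcome group;
- report CT accuracy overall, and separately for contrast and non-contrast scans, with confidence intervals;
- report the AUC of contrast status alone beside the AUC of the CT model.

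The overall result should remain, because section 4.2 expressly includes both scan types. Restricting the main CT result to one type would narrow that population.

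**Cost:** one or two extra fields collected retrospectively, and one or two tables. The statistical price is wider intervals within each contrast stratum. How wide cannot be stated, because the number of patients with CT is not given. Indication may be missing for some scans, and the share missing should be reported.
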